### 6.6.3 Dose Modification of mRNA-5671/V941

Individual participant dose modifications of mRNA-5671/V941 (dose increases or dose reductions) are not permitted in the study, unless the participant is crossing over to Arm B, which may result in a reduced dose of mRNA-5671/V941, if a lower dose is determined to be the safe dose in combination. If the participant requires a delay in pembrolizumab dosing, administration of mRNA-5671/V941 may also be delayed based on an assessment of relationship to study treatment(s). Any irAEs associated with mRNA-5671/V941 will follow the same guidelines presented in Table 5.

# 6.6.4 Immune-Related Events and Dose Modification (Withhold, Treat, Discontinue)

# Dose Modification and Toxicity Management for Immune-related AEs Associated with Pembrolizumab or Study Interventions

AEs associated with pembrolizumab or study interventions exposure may represent an immune-related response. These irAEs may occur shortly after the first dose or several months after the last dose of pembrolizumab or study interventions treatment and may affect more than one body system simultaneously. Therefore, early recognition and initiation of treatment is critical to reduce complications. Based on existing clinical study data, most irAEs were reversible and could be managed with interruptions of pembrolizumab or study interventions, administration of corticosteroids and/or other supportive care. For suspected irAEs, ensure adequate evaluation to confirm etiology or exclude other causes. Additional procedures or tests such as bronchoscopy, endoscopy, skin biopsy may be included as part of the evaluation.

Dose Modification and Toxicity Management Guidelines for irAEs associated with pembrolizumab monotherapy, coformulations, or IO combinations are provided in Table 5.

Table 5 Dose Modification and Toxicity Management Guidelines for Immune-related Adverse Events Associated with Pembrolizumab Monotherapy, Coformulations or IO Combinations

### General instructions:

- 1. Severe and life-threatening irAEs should be treated with IV corticosteroids followed by oral steroids. Other immunosuppressive treatment should begin if the irAEs are not controlled by corticosteroids.
- 2. Pembrolizumab monotherapy, coformulations or IO combinations must be permanently discontinued if the irAE does not resolve or the corticosteroid dose is not ≤10 mg/day within 12 weeks of the last treatment.
- 3. The corticosteroid taper should begin when the irAE is  $\leq$  Grade 1 and continue at least 4 weeks.
- 4. If pembrolizumab monotherapy, coformulations or IO combinations have been withheld, treatment may resume after the irAE decreased to ≤ Grade 1 after corticosteroid taper.

irAEs	Toxicity Grade (CTCAEv4.0)	Action With Pembrolizumab Monotherapy, Coformulations or IO Combinations	Corticosteroid and/or Other Therapies	Monitoring and Follow-up
Pneumonitis	Grade 2	Withhold	Administer corticosteroids     (initial dose of 1-2 mg/kg     prednisone or equivalent)	
 
Monitor participants for signs and symptoms of pneumonitis
 
Evaluate participants with suspected pneumonitis with
 

	Recurrent Grade 2 or Grade 3 or 4	Permanently discontinue	followed by taper	radiographic imaging and initiate corticosteroid treatment  • Add prophylactic antibiotics for opportunistic infections
Diarrhea / Colitis	Grade 2 or 3	Withhold	Administer corticosteroids (initial dose of 1-2 mg/kg prednisone or equivalent) followed by taper	Monitor participants for signs and symptoms of enterocolitis (ie, diarrhea, abdominal pain, blood or mucus in stool with or without fever) and of bowel perforation (ie, peritoneal signs and ileus)

Confidential

irAEs	Toxicity Grade (CTCAEv4.0)	Action With Pembrolizumab Monotherapy, Coformulations or IO Combinations	Corticosteroid and/or Other Therapies	Monitoring and Follow-up
	Recurrent Grade 3 or Grade 4	Permanently discontinue		
 
Participants with ≥Grade 2 diarrhea suspecting colitis should consider GI consultation and performing endoscopy to rule out colitis
 
Participants with diarrhea/colitis should be advised to drink liberal quantities of clear fluids. If sufficient oral fluid intake is not feasible, fluid and electrolytes should be substituted via IV infusion.
 

AST / ALT Elevation or Increased Bilirubin	Grade 2	Withhold	Administer corticosteroids (initial dose of 0.5-1 mg/kg prednisone or equivalent) followed by taper	Monitor with liver function tests (consider weekly or more frequently until liver enzyme value returned to baseline or is stable)
	Grade 3 or 4	Permanently discontinue	Administer corticosteroids (initial dose of 1-2 mg/kg prednisone or equivalent) followed by taper	
T1DM or Hyperglycemia	New onset T1DM or Grade 3 or 4 hyperglycemia associated with evidence of β- cell failure	Withhold a	Initiate insulin replacement therapy for participants with T1DM     Administer antihyperglycemic in participants with hyperglycemia	Monitor participants for hyperglycemia or other signs and symptoms of diabetes
Hypophysitis	Grade 2	Withhold	Administer corticosteroids and initiate hormonal replacements as clinically	Monitor for signs and symptoms of hypophysitis (including hypopituitarism and adrenal insufficiency)
	Grade 3 or 4	Withhold or permanently discontinue a	indicated	

C Confidential

#### PRODUCT: V941

### PROTOCOL/AMENDMENT NO.: 001-08

irAEs	Toxicity Grade (CTCAEv4.0)	Action With Pembrolizumab Monotherapy, Coformulations or IO Combinations	Corticosteroid and/or Other Therapies	Monitoring and Follow-up
Hyperthyroidism	Grade 2	Continue	Treat with non-selective beta- blockers (eg, propranolol) or thionamides as appropriate	Monitor for signs and symptoms of thyroid disorders
	Grade 3 or 4	Withhold or	tinonamides as appropriate	
		Permanently discontinue a		
Hypothyroidism	Grade 2-4	Continue	Initiate thyroid replacement hormones (eg, levothyroxine or liothyronine) per standard of care	Monitor for signs and symptoms of thyroid disorders
Nephritis and renal dysfunction	Grade 2	Withhold	Administer corticosteroids (prednisone 1-2 mg/kg or	Monitor changes of renal function
renar dystanetron	Grade 3 or 4	Permanently discontinue	equivalent) followed by taper	
Myocarditis	Grade 1	Withhold	Based on severity of AE administer corticosteroids	Ensure adequate evaluation to confirm etiology and/or exclude other causes
	Grade 2, 3 or 4	Permanently discontinue		

irAEs	Toxicity Grade (CTCAEv4.0)	Action With Pembrolizumab Monotherapy, Coformulations or IO Combinations	Corticosteroid and/or Other Therapies	Monitoring and Follow-up
All Other irAEs	Persistent Grade 2	Withhold	Based on severity of AE administer corticosteroids	Ensure adequate evaluation to confirm etiology or exclude other causes
	Grade 3	Withhold or discontinue b		
	Recurrent Grade 3 or Grade 4	Permanently discontinue		

AE(s)=adverse event(s); ALT= alanine aminotransferase; AST=aspartate aminotransferase; CTCAE=Common Terminology Criteria for Adverse Events; DRESS=Drug Rash with Eosinophilia and Systemic Symptom; GI=gastrointestinal; IO=immuno-oncology; ir=immune related; IV=intravenous; SJS=Stevens-Johnson Syndrome; T1DM=type 1 diabetes mellitus; TEN=Toxic Epidermal Necrolysis; ULN=upper limit of normal.

## Note: Non-irAE will be managed as appropriate, following clinical practice recommendations.

- a The decision to withhold or permanently discontinue pembrolizumab monotherapy, coformulations or IO combinations is at the discretion of the investigator or treating physician. If control achieved or ≤ Grade 2, pembrolizumab monotherapy, coformulations or IO combinations may be resumed.
- b Events that require discontinuation include, but are not limited to: Guillain-Barre Syndrome, encephalitis, myelitis, DRESS, SJS, TEN and other clinically important irAEs (eg, vasculitis and sclerosing cholangitis).

V941-001-08 FINAL PROTOCOL

# **Dose Modification and Toxicity Management of Infusion Reactions Related to Pembrolizumab**

Pembrolizumab may cause severe or life-threatening infusion-reactions including severe hypersensitivity or anaphylaxis. Signs and symptoms usually develop during or shortly after drug infusion and generally resolve completely within 24 hours of completion of infusion. Dose modification and toxicity management guidelines on pembrolizumab associated infusion reaction are provided in Table 6.

Table 6 Guidelines for Pembrolizumab Infusion Reaction Dose Modification and Treatment

Treatment	Premedication at Subsequent Dosing
Increase monitoring of vital signs as medically indicated until the participant is deemed medically stable in the opinion of the investigator	None
Stop Infusion Additional appropriate medical therapy may include but is not limited to:  IV fluids Antihistamines NSAIDs Acetaminophen Narcotics Increase monitoring of vital signs as medically indicated until the participant is deemed medically stable in the opinion of the investigator.  If symptoms resolve within 1 hour of stopping drug infusion, the infusion may be restarted at 50% of the original infusion rate (eg, from 100 mL/hr to 50 mL/hr). Otherwise dosing will be held until symptoms resolve and the participant should be premedicated for the next scheduled dose.  Participants who develop Grade 2 toxicity despite adequate premedication should be permanently discontinued from further study	Participant may be premedicated 1.5 h (±30 minutes) prior to infusion of pembrolizumab with: Diphenhydramine 50 mg PO (or equivalent dose of antihistamine). Acetaminophen 500 to 1000 mg PO (or equivalent dose of analgesic).
	Increase monitoring of vital signs as medically indicated until the participant is deemed medically stable in the opinion of the investigator  Stop Infusion  Additional appropriate medical therapy may include but is not limited to:  IV fluids  Antihistamines  NSAIDs  Acetaminophen  Narcotics  Increase monitoring of vital signs as medically indicated until the participant is deemed medically stable in the opinion of the investigator.  If symptoms resolve within 1 hour of stopping drug infusion, the infusion may be restarted at 50% of the original infusion rate (eg, from 100 mL/hr to 50 mL/hr). Otherwise dosing will be held until symptoms resolve and the participant should be premedicated for the next scheduled dose.  Participants who develop Grade 2 toxicity despite adequate premedication should be

81

NCI CTCAE Grade	Treatment	Premedication at Subsequent Dosing
Grades 3 or 4	Stop Infusion.	No subsequent dosing
Grade 3:	Additional appropriate medical therapy may	Two subsequent desing
Prolonged (ie, not rapidly	include but is not limited to:	
responsive to symptomatic	Epinephrine**	
medication and/or brief	IV fluids	
interruption of infusion);	Antihistamines	
recurrence of symptoms	NSAIDs	
following initial improvement;	Acetaminophen	
hospitalization indicated for	Narcotics	
other clinical sequelae (eg,	Oxygen	
renal impairment, pulmonary	Pressors	
infiltrates)	Corticosteroids	
Grade 4:	Increase monitoring of vital signs as	
Life-threatening; pressor or	medically indicated until the participant is	
ventilatory support indicated	deemed medically stable in the opinion of the	
ventuatory support materica	investigator.	
	Hospitalization may be indicated.	
	**In cases of anaphylaxis, epinephrine	
	should be used immediately.	
	Participant is permanently discontinued from	
	further study drug treatment.	

Appropriate resuscitation equipment should be available at the bedside and a physician readily available during the period of drug administration.

For further information, please refer to the Common Terminology Criteria for Adverse Events v4.0 (CTCAE) at http://ctep.cancer.gov

## **Other Allowed Dose Interruption for Pembrolizumab**

Pembrolizumab may be interrupted for situations other than treatment-related AEs such as medical / surgical events or logistical reasons not related to study therapy. Participants should be placed back on study therapy within 3 weeks of the scheduled interruption, unless otherwise discussed with the Sponsor. The reason for interruption should be documented in the participant's study record.

## 6.7 Intervention After the End of the Study

There is no study-specified intervention following the end of the study.

Participants on active treatment with pembrolizumab monotherapy in the post-treatment phase are discontinued and may be enrolled in to a pembrolizumab extension study.

## 6.8 Clinical Supplies Disclosure

V941-001-08 FINAL PROTOCOL

This study is open-label; therefore, the participant, the study site personnel, the Sponsor, and/or designee are not blinded. Study intervention (name, strength, or potency) is included in the label text; random code/disclosure envelopes or lists are not provided.

# 7 DISCONTINUATION OF STUDY INTERVENTION AND PARTICIPANT WITHDRAWAL

# 7.1 Discontinuation of Study Intervention

Discontinuation of study intervention does not represent withdrawal from the study.

As certain data on clinical events beyond study intervention discontinuation may be important to the study, they must be collected through the participant's last scheduled follow-up, even if the participant has discontinued study intervention. Therefore, all participants who discontinue study intervention prior to completion of the protocol-specified treatment period will still continue to participate in the study as specified in Section 1.3 and Section 8.11.4.

Participants may discontinue study intervention at any time for any reason or be dropped from the study intervention at the discretion of the investigator should any untoward effect occur. In addition, a participant may be discontinued from study intervention by the investigator or the Sponsor if study intervention is inappropriate, the study plan is violated, or for administrative and/or other safety reasons. Specific details regarding procedures to be performed at study intervention discontinuation are provided in Section 8.1.9.

A participant must be discontinued from study intervention but continue to be monitored in the study for any of the following reasons:

- The participant or participant's legally acceptable representative requests to discontinue study intervention.
- The participant interrupts study intervention administration for more than 12 consecutive weeks (exception if the Sponsor approves treatment continuation).
- The participant has a medical condition or personal circumstance which, in the opinion of the investigator and/or Sponsor, placed the participant at unnecessary risk from continued administration of study intervention.
- The participant has a confirmed positive serum pregnancy test.
- Unacceptable adverse experiences as described in Section 8.4.
- Intercurrent illness other than another malignancy that prevents further administration of study intervention.
- Confirmed radiographic disease progression outlined in Section 8.2.1.5 (exception if the Sponsor approves treatment continuation)
- Any progression or recurrence of any malignancy, or any occurrence of another malignancy that requires active treatment
- Noncompliance with study intervention or procedure requirements

- Recurrent Grade 2 pneumonitis
- Completion of 35 treatments (approximately 2 years) with pembrolizumab

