#### **Diagnostic Assessments**

- 12. Has a diagnosis of immunodeficiency or is receiving chronic systemic steroid therapy (in dosing exceeding 10 mg daily of prednisone equivalent) or any other form of immunosuppressive therapy within 7 days prior the first dose of study drug.
- 13. Has a known additional malignancy that is progressing or has required active treatment within the past 2 years.
  - Note: Participants with basal cell carcinoma of the skin, squamous cell carcinoma of the skin, or carcinoma in situ (eg, breast carcinoma, cervical cancer in situ) that have undergone potentially curative therapy are not excluded.
- 14. Has known active CNS metastases and/or carcinomatous meningitis. Participants with previously treated brain metastases may participate provided they are radiologically stable, (ie, without evidence of progression) for at least 4 weeks by repeat imaging (note that the repeat imaging should be performed during study screening), clinically stable and without requirement of steroid treatment for at least 14 days prior to first dose of study intervention.

- 15. Has severe hypersensitivity (≥Grade 3) to pembrolizumab and/or any of its excipients.
- 16. Has a history of (non-infectious) pneumonitis that required steroids or has current pneumonitis.
- 17. Has a known history of Hepatitis B (defined as Hepatitis B surface antigen [HBsAg] reactive) or known active Hepatitis C virus (defined as HCV RNA [qualitative] is detected) infection.

Note: No testing for Hepatitis B and Hepatitis C is required unless mandated by local health authority.

18. Has a known history of HIV.

Note: No testing for HIV is required unless mandated by local health authority.

19. Has a known psychiatric or substance abuse disorder that would interfere with cooperating with the requirements of the study.

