## **8.2.1.4 RECIST 1.1 Assessment of Disease**

RECIST 1.1 will be used by investigator assessment as the primary measure for assessment of tumor response, date of disease progression, and as a basis for all protocol guidelines related to disease status (eg, discontinuation of study intervention). Although RECIST 1.1

V941-001-08 FINAL PROTOCOL 24-MAR-2022

references a maximum of 5 target lesions in total and 2 per organ, this protocol allows a maximum of 10 target lesions in total and 5 per organ, if clinically relevant to enable a broader sampling of tumor burden.

90

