### 8.2.1.5 iRECIST Assessment of Disease

iRECIST is based on RECIST 1.1, but adapted to account for the unique tumor response seen with immunotherapeutic drugs. iRECIST will be used by the investigator to assess tumor response and progression, and make treatment decisions. When clinically stable, participants should not be discontinued until progression is confirmed by the investigator, working with local radiology, according to the rules outlined in Appendix 8. This allowance to continue treatment despite initial radiologic PD takes into account the observation that some participants can have a transient tumor flare in the first few months after the start of immunotherapy, and then experience subsequent disease response. This data will be captured in the clinical database.

Clinical stability is defined as the following:

- Absence of symptoms and signs indicating clinically significant progression of disease
- No decline in ECOG performance status
- No requirements for intensified management, including increased analgesia, radiation, or other palliative care

Any participant deemed clinically unstable should be discontinued from study intervention at site-assessed first radiologic evidence of PD, and is not required to have repeat tumor imaging for confirmation of PD by iRECIST.

If the investigator decides to continue treatment, the participant may continue to receive study intervention and the tumor assessment should be repeated 4 to 8 weeks later to confirm PD by iRECIST, per investigator assessment. In order to continue to receive study intervention after initial radiologic PD, the participant must sign an additional informed consent form (see Section 8.1.1.1).

If repeat imaging does not confirm PD per iRECIST, as assessed by the investigator, and the participant continues to be clinically stable, study intervention may continue and follow the regular imaging schedule. If PD is confirmed, participants will be discontinued from study intervention.

If a participant has confirmed radiographic progression (iCPD) as defined in Appendix 8, study intervention should be discontinued; however, if the participant is achieving a clinically meaningful benefit, an exception to continue study intervention may be considered following consultation with the Sponsor. In this case, if study intervention is continued, tumor imaging should continue to be performed following the intervals as outlined in Section 8.2.1.2.

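### A mandatory stop bullet in Section 7.1 covers progression of the study cancer as worded, and so contradicts the confirmed-progression rule beside it (minor)

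*Combined protocol and SAP*

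**What the plan says.** Section 7.1 opens its list with "A participant must be discontinued from study intervention but continue to be monitored in the study for any of the following reasons". Any one entry is enough. Three consecutive entries matter here:

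- The first deals with other illness and sets second cancers apart: "Intercurrent illness other than another malignancy that prevents further administration of study intervention".
- The second deals with the study cancer and points to the iRECIST section: "Confirmed radiographic disease progression outlined in Section 8.2.1.5 (exception if the Sponsor approves treatment continuation".
- The third, which is the one at issue, reads: "Any progression or recurrence of any malignancy, or any occurrence of another malignancy that requires active treatment".

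Section 8.2.1.5 sets the rule for progression of the study cancer: "When clinically stable, participants should not be discontinued until progression is confirmed by the investigator, working with local radiology". It adds a consent condition: "In order to continue to receive study intervention after initial radiologic PD, the participant must sign an additional informed consent form". Clinically unstable participants stop at first radiologic progression. After confirmed progression, stopping is the default, but the Sponsor may agree to continuation. Section 8.2.1.2 and Table 7 leave treatment between first and confirmed progression to the investigator.

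Section 4.1 and inclusion criterion 11 (Section 5.1) allow Arm A participants with RECIST 1.1 progression to cross over with Sponsor approval. Those who have had fewer than 9 vaccine doses may complete the remainder together with pembrolizumab.

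Section 8.2.1.4 describes investigator-assessed RECIST 1.1 "as a basis for all protocol guidelines related to disease status (eg, discontinuation of study intervention".

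**The concern.** The third entry refers to any malignancy in its first half and to another malignancy only in its second. The first half therefore includes the cancer under study. It carries neither the confirmation step nor the Sponsor exception of the entry before it. Reading the closing qualifier about active treatment across both halves does not help, because it does not exclude the study cancer either.

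A site that applied the entry literally would have to stop a clinically stable participant at first, unconfirmed progression. A site that followed 8.2.1.5 could keep treating the same participant. The two sites would differ in when treatment ends. Under Appendix 8 there is no separate iRECIST assessment until RECIST 1.1 progression has occurred, so what happens after that point is all that can separate iRECIST results from RECIST 1.1 results. At stake are time on treatment and ORR and PFS by iRECIST.

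**Working it through.** No figure in the plan depends on this point, so the check is to apply each rule to the same participant.

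| Situation | 7.1, confirmed-progression entry | 7.1, any-malignancy entry as worded | Other provisions |
|---|---|---|---|
| Clinically stable, first unconfirmed progression of the study cancer | Not triggered | Must stop | 8.2.1.2, 8.2.1.5, Table 7: may continue, with extra consent (8.1.1.1, 8.2.1.5) |
| Confirmed progression, Sponsor agrees to continue | Exception applies | Must stop | 8.2.1.5, Table 7: may continue |
| Arm A, RECIST 1.1 progression before 9 doses, Sponsor approves crossover | Not triggered, or exception applies | Must stop | 4.1, 5.1 criterion 11, 1.3.3: remaining vaccine doses may be given with pembrolizumab |
| Clinically unstable, first progression | Not triggered | Must stop | 8.2.1.5, Table 7: stop |
| New second cancer needing treatment | Not relevant | Must stop | No conflict |

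The any-malignancy entry contradicts other text in the first three rows. In the fourth it agrees with 8.2.1.5. The fifth is the case it appears to have been written for. Taken literally, it also makes the confirmed-progression entry redundant and its Sponsor exception void.

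Reach into the analyses:

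- **RECIST 1.1 ORR (9.4.1).** The entry takes effect only once progression has occurred, so what follows has essentially no bearing on whether a RECIST 1.1 response was reached before it.
- **Futility rule (9.7) and power statement (9.9).** Both rest on response counts or rates, and 9.4.1 defines ORR by RECIST 1.1. They are essentially unaffected for the same reason.
- **DLT rules (6.6.2).** These concern treatment-related toxicity in the first 21 days. The first scheduled on-study scan is at 63 ± 7 days, so no earlier than 63 − 7 = 56 days.
- **iRECIST ORR and PFS (Section 3).** These can be affected, because they depend on what happens after first RECIST 1.1 progression.

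**The case against.** The strongest reply is that nobody would read the entry literally. The entry before it deals specifically with progression of the study cancer. The one before that sets other malignancies aside for separate handling. Exclusion criterion 13 uses similar language for second cancers: "Has a known additional malignancy that is progressing or has required active treatment within the past 2 years". The synopsis, 8.2.1.2, 8.2.1.5, Table 7 and Appendix 8 all provide for confirmation. This stands as evidence of intent: second cancers were probably meant, and most sites would probably follow 8.2.1.5. But no section states the carve-out, and in a mandatory list where any single entry suffices, sites should not have to infer it.

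A second reply is that investigators may already stop a stable participant at first progression (4.1, Table 7). That also stands, and correcting the entry would not make sites uniform. It does not dispose of the point, because the literal entry turns a permission into an obligation and removes the Sponsor exception.

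A reader might also infer that 8.2.1.4 flatly contradicts 8.2.1.5 by making RECIST 1.1 the sole ground for stopping. The text does not go that far. It calls RECIST 1.1 a basis, not the only one. Since iRECIST is built on RECIST 1.1, the two sections can largely be reconciled: RECIST 1.1 progression is the trigger, and iRECIST adds confirmation for stable participants. A clarification there is optional.

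A reader might further infer that the entry overrides Section 6.5.1 on local treatment of isolated progressing lesions. That section concerns participants whose baseline disease is improving, which need not be overall progression, so it is not counted as a conflict.

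**Conclusion.** The entry is wrong as written, and the matter is minor. An operative stop rule includes the study cancer in its wording and conflicts with the entry before it, with 8.2.1.2, 8.2.1.5 and Table 7, with the consent for treatment beyond progression, and with Arm A crossover.

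The size of the consequence cannot be estimated. It depends on how sites read the entry, and the documents do not say. If every site follows 8.2.1.5, it is zero.

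A reader might take the 7% melanoma pseudo-progression figure in Section 4.2.1.1.2 and infer a loss of up to 7 percentage points of iRECIST ORR. The documents do not support that as an effect size. The figure comes from melanoma, whereas Part 2 enrols lung, colorectal and pancreatic cancers. Resolved pseudo-progression may be only stable disease (Appendix 8). The contrast would also set every site stopping at first progression against every site treating on, although investigator discretion makes the latter unrealistic.

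Section 9.4.1 names only RECIST 1.1 for ORR, while Section 3 also lists iRECIST. That is a separate alignment matter, since 4.1 already states that iRECIST will be used as well, and it adds nothing to this point.

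**What to change.** Reword the 7.1 entry to: *Any occurrence, progression or recurrence of a malignancy other than the study cancer that requires active treatment.* Progression of the study cancer is then governed only by the preceding entry and 8.2.1.5.

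Optionally, add to 8.2.1.4 that discontinuation for progression follows 8.2.1.5, leaving RECIST 1.1 as the primary measure of response and of the date of progression.

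The cost is one sentence, or two with the optional clarification. No scans, visits or participants are added, and investigator discretion at first progression is untouched. Amendment 8 prepares for close-out, so the practical benefit is limited to participants still on study intervention.
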